### **14 STUDY CONDUCT, OVERSIGHT, AND QUALITY CONTROL AND ASSURANCE**

#### **14.1 Protocol Amendments**

The protocol, CRFs, informed consent form, other participant information, and other clinical investigation documents shall be amended as needed throughout the clinical investigation. A justification statement shall be included with each amended section of a document. Proposed amendments to the protocol shall be agreed upon between the Sponsor and Principal Investigator, or the coordinating investigator. The amendments to the protocol and the participant's informed consent form shall be notified to, or approved by, the IRB and regulatory authorities, as required. For non-substantial changes [e.g. minor logistical or administrative changes, change of monitor(s), telephone numbers, renewal of insurance] not affecting the rights, safety and well-being of human participants or not related to the clinical investigation objectives or endpoints, a simple notification to the IRB and, where appropriate, regulatory authorities can be sufficient. The version number and date of amendments shall be documented.

#### **14.2 Termination of Study or Study Site Participation**

The Sponsor may terminate the study at any time. If the study is terminated prior to the completion of expected enrollment for any reason, all participating centers will be notified within five (5) working days. All participants already enrolled will continue to be followed for the planned course of study described in this protocol. The study shall be terminated following the final follow-up visit of the last enrolled participant.

The Sponsor reserves the right to terminate study site participation and remove appropriate study materials at any time. Specific instances that may precipitate such termination include but are not limited to the following:

- Repeated failure to complete Electronic Case Report Forms, in a timely manner
- Failure to attempt to obtain Informed Consent from the legally authorized representative
- Failure to report Serious Adverse Events in a timely manner
- Loss of or unaccountable investigational device inventory
- Repeated protocol violations
- Failure to enroll an adequate number of participants

The site Investigator may also discontinue study participation with suitable written notice to the Sponsor.

#### **14.3 Publication Policy**

The Sponsor will submit results to the [clinicaltrials.gov](https://clinicaltrials.gov) registry in accordance with the International Committee of Medical Journal Editors and applicable US laws and regulations. Study results will be published regardless of the outcome as required by law. The Sponsor accepts the obligation to facilitate publication of medically important clinical data in a timely, objective, accurate, and balanced manner, regardless of the outcome of this trial. To ensure that an accurate record of the study data is presented to the public, the Sponsor understands the need to allow sufficient time, for careful preparation, analysis, interpretation, and review of study data and reports prior to their dissemination.

This trial will be registered at the National Institutes of Health National Library of Medicine's ClinicalTrials.gov website. Results from this trial will be submitted to ClinicalTrials.gov. The NCT number is pending.

All information regarding the Quanta SC+ DDS supplied by the Sponsor to the Investigator or generated as a result of any clinical studies is privileged and confidential information belonging to the Sponsor. The Investigator agrees to use the Sponsor's confidential information solely to accomplish the study and will not use such information for any other purposes without the prior written consent of the Sponsor. The Investigator shall provide the Sponsor with complete and accurate data obtained during the study. The information obtained from the clinical study will be used towards the development of the Quanta SC+ DDS and may be disclosed by the Sponsor to regulatory authorities, other Investigators, corporate partners, or consultants as required.

It is anticipated that the results of this study may be presented at scientific meetings and/or published in peer reviewed scientific or medical journals. All publications and presentations must be approved in advance, at the sole discretion of the Sponsor. Subsequently, individual Investigators may publish results from the study in compliance with their agreement with the Sponsor. A pre-publication manuscript is to be provided to the Sponsor at least 30 days prior to the submission of the manuscript to a publisher. All publications and presentations must be approved in writing by the Sponsor before public disclosure.

#### **14.4 Site and Investigator Selection**

The Sponsor selects qualified investigators with appropriate experience at health care facilities with adequate resources to participate in this study. Investigational sites will be selected using combined current assessments of site and investigator qualifications.

#### 14.5 Investigator Responsibilities

Prior to participation in the Study, the appointed Principal Investigator at the Investigational Site must obtain written approval from the applicable IRB. This approval must be in the Principal Investigator's name and a copy sent to the Sponsor or designee along with the IRB approved Informed Consent Form, and the signed Clinical Study Agreement, prior to first shipment of the investigational device.

The Principal Investigator must also:

- Conduct the study in accordance with the study protocol, the signed Clinical Study Agreement, applicable regulations (including 21 CFR Parts 11, 50, 54, 56 and 812), the Declaration of Helsinki, Good Clinical Practices, any conditions of approval from the IRB or FDA, and ISO 14155;
- agree to participate in a device training program prior to study initiation, as applicable;
- provide a copy of a Financial Disclosure form that summarizes financial interest in the Sponsor. In addition, the Sponsor will be notified if disclosed financial information changes at any time during the clinical investigation or up to one year following the closure of the study;
- provide the Sponsor with curriculum vitae, information regarding previous clinical investigation experiences (including investigations or research that was terminated);
- assure that no study assessments or procedures occur until IRB approval has been obtained;
- assure that informed consent is obtained from each participant prior to enrollment, using the IRB and Sponsor approved forms;
- ensure that investigational devices are only used by approved, trained investigators in participants who meet all study inclusion criteria and no study exclusion criteria;
- supervise all testing of the device involving human participants;
- complete all eCRFs and study documentation and relevant imaging assessments, and promptly forward to the Sponsor or designee for data management;
- report all adverse events, non-medical complaints and non-compliance to Sponsor according to the protocol and regulatory requirements;
- provide all required data and agree to source document verification of study data with participant's medical records;
- allow staff of the Sponsor or designee, as well as representatives from regulatory bodies, to review, inspect and copy any documents pertaining to this clinical investigation; and
- oversee retention of required records and documents related to the investigation.

The Principal Investigator may delegate one or more of the above functions to an associate or Sub-Investigator. However, the Principal Investigator retains overall responsibility for proper conduct of the study, including obtaining and documenting participant informed consent, compliance with the

study protocol, and collection of all required data. Delegated tasks must be documented on a Delegation Log.

#### **14.6 Protocol Deviations**

An Investigator is not allowed to deviate from the Protocol if the deviation affects participant's rights, safety and wellbeing, or the scientific integrity of the clinical investigation. Under emergency circumstances, deviations from the Protocol to protect the rights, safety and well-being of human participants may proceed without prior approval of the Sponsor and the IRB. Such deviations shall be documented and reported to the Sponsor and the IRB as soon as possible.

A protocol deviation is a failure to comply with the requirements specified within this clinical study protocol. Examples of protocol deviations may include enrollment of a study participant who does not meet all of the enrollment criteria specified in the protocol or instances where participants miss study visits without documentation. Each investigator shall conduct this clinical study in accordance with this clinical study protocol, regulatory body regulations, ISO guidelines, Good Clinical Practices, and any conditions of approval imposed by their IRB.

The protocol deviations for this protocol consist of, but not limited to, the following:

- Failure to obtain participant's informed consent prior to any study-related activities;
- Failure to conduct protocol required clinical follow-ups;
- Failure to conduct protocol required clinical follow-ups within time windows; and
- Failure to report serious adverse events according to protocol requirements.

In the event of any deviation from the protocol, the Investigator will be notified of the site's non-compliance. Corrective actions may be required, if necessary. Continued protocol deviations despite re-education of the study site personnel or persistent protocol deviation may result in termination of the site's study participation. Participants enrolled at these sites will continue to be followed per the clinical protocol.

Investigators must report protocol deviations to the Sponsor by entering data into the eCRF. Any protocol deviations that affect the rights, safety or well-being of the participant or the scientific integrity of the clinical investigation, including those which occur under emergency circumstances must be reported within 24 hours to the Sponsor and IRB if required by the IRB.

#### **14.7 Safety and Clinical Events Committee**

An independent safety and clinical events committee (SCEC) will be created, chartered, and maintained while any adverse events are being collected or participants are receiving study treatment to oversee trial safety and event handling. The SCEC will review all AEs reported in the primary study and SAEs reported in the extended treatment phase. Sponsor will continue to monitor AEs that are reported during the extended treatment phase and will report the events to applicable regulatory authorities and to IRBs as required. The SCEC will comprise three nephrologists (MDs or DOs) with experience in hemodialysis, including at least one with significant experience in home hemodialysis or peritoneal dialysis, and a human factors engineer. While the investigator will assign an initial finding of device relatedness for AEs in the primary study phase, the SCEC will review these events and will adjudicate, providing the final determination for the study record.

The human factors engineer will participate when a device related event is identified (please see [Appendix](#)). When the event is related to device or user error, the human factors engineer will initiate an investigation with the clinical site to obtain information to do a root cause analysis. Any such events will be fully reviewed by the human factors engineer and presented to the SCEC for adjudication to determine whether they are device related.

The SCEC will have authority to recommend after periodic review of data or after evaluating serious AEs that have been brought to its attention, that the trial continue with no changes, continue with changes to the protocol or other operational documents and procedures, or be suspended.

In the primary study, the SCEC will be blinded to whether events occurred during the in-clinic or home phase of the trial. They will not be told information about event dates or other information that would lead to deduction of the time the participant had been in the trial, whether the patient or caregiver or a clinic health care provider performed the treatment, the level of training the participant had received, or similar elements. AE narratives and other case information provided to the SCEC will be reviewed to ensure this information is masked. In the extended treatment phase, the SCEC will not be blinded when reviewing and adjudicating SAEs as all events would occur while the participant is at home.

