## 6.2.2 Secondary Endpoints

### Safety:

- Number of serious adverse events (SAEs) per 100 treatments occurring in the home phase of the study, compared with those occurring in the in-clinic phase.
- Number of device-related AEs and SAEs per 100 treatments in the home phase of the study, compared with those occurring in the in-clinic phase.
- Additional adverse events of special interest:
  - Individual components of the primary safety endpoint
  - Air in blood tubing that cannot be resolved through usual procedures.
  - Significantly elevated venous (>250 mmHg) or negative arterial (>100 mmHg) pressures during three (3) consecutive treatments.
  - Intradialytic hypotension, as defined by treatments during which hypotensive symptoms led to either lowering the ultrafiltration rate or saline administration.
  - Post-dialysis (30 minutes) systolic blood pressure <90 mmHg or systolic blood pressure >180 mmHg following two (2) consecutive treatments.

The following biochemistry and hematology laboratory values will be collected and compared to target ranges from clinical practice guidelines.

Biochemistry: assessments of pre-treatment plasma at visits C1, C2, C4, C6, C8, H2, , H4, H6 and H8/Withdrawal:

- sodium (Na) (target range, 135-145 mEq/L)
- urea (BUN)
- potassium (K) (target range, 3.5-5.5 mEq/L)
- creatinine (Cr)
- bicarbonate (HCO3) (target range,  $\geq 22$  mEq/L)
- magnesium (Mg)
- phosphate (Phos) (target range, 3.5-5.5 mg/dL)
- chloride (Cl)
- calcium (Ca) (target range, 8.4-9.5 mg/dL)
- albumin (Alb) (target range,  $\geq 3.5$  g/dL)
- iron (Fe)
- transferrin saturation (TS) (target range, >20%)
- total protein (TP)
- ferritin (Fn) (target range, >200 ng/mL)
- alkaline phosphatase (ALP)
- parathyroid hormone (PTH) (target range, 150-600 pg/mL)
- total iron binding capacity (TIBC)
- aspartate transaminase (AST)
- alanine aminotransferase (ALT)

Hematology: assessments of pre-treatment blood at visits C1, C2, C4, C6, C8, H2, H4, H6 and H8/Withdrawal:

- hemoglobin (Hb)
- hematocrit (Hct)
- white cell count (WBC)
- platelet count (PC)
- reticulocyte Count (RC)

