  - the HF specialist will work closely with the site staff to ensure any HF work is performed without interfering with the primary objective of the IDE clinical trial
3. The HF specialist will review and analyse the data collected, including the event log information and subjective feedback collected during follow-up activities, to identify the root cause(s) of any use-related errors associated with critical tasks. The root cause analysis will aim to identify what, including any aspect of the SC+ user interface, home use environment, or other factor(s), contributed to the error.
4. The HF specialist will document the identified root causes in a format that will be determined by the CEC.
5. The CEC and other Quanta representatives, as appropriate, will be responsible for determining if any further risk control measures will need to be implemented.

Device error events that are deemed non-critical per the use-related risk analysis (i.e., errors related to use steps not associated with a potential for serious harm) are out of scope of the IDE clinical trial’s HF activities, in line with FDA’s HFE guidance for medical devices.

The following event framework is for use in approaching and categorising potential events that would require investigation by the Safety Team. It is derived from definitions defined in part by standards and in part by the Sponsor based on previous assessments, submissions and business definitions.

Level 1: Protective System Performance
 
Did a device failure of its constructional or functional safety compromise a risk control measure of the Hazard Analysis?
		
If Yes, investigate immediately with Sponsor.
 
If No, move to Level 2.

Level 2: Essential Performance
 
In accordance with IEC 60601-2-16, did the device fail to meet the tolerances specified by the Sponsor under normal conditions:
 
 
• Blood flow rate
 
• Dialysis fluid flow rate
 
• Net fluid removal
 
• Dialysis time
 
• Dialysis fluid composition
 
• Dialysis fluid temperature
 
		
If Yes, investigate immediately with Sponsor.
 
If No, move to Level 3.

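### The SCEC is declared blinded to phase and operator, but its human factors engineer must investigate device and user errors with the site, so the blind cannot hold for one of four members and is not shown to be protected for the other three

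*Protocol*

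**What the plan says.** Protocol section 14.7 sets up an SCEC of three nephrologists, "including at least one with significant experience in home hemodialysis or peritoneal dialysis, and a human factors engineer". It states that "the SCEC will be blinded to whether events occurred during the in-clinic or home phase of the trial". Event dates and training level are also withheld, as is "whether the patient or caregiver or a clinic health care provider performed the treatment". Narratives and other case material are to be checked for masking before the committee receives them. The investigator makes the first call on device-relatedness, and the SCEC's call is the final one.

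The same section says that, for device or user error, "the human factors engineer will initiate an investigation with the clinical site to obtain information to do a root cause analysis". These events are then to be "fully reviewed by the human factors engineer and presented to the SCEC for adjudication to determine whether they are device related".

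The Appendix on device- and user-related errors describes the human factors work. The specialist reviews device error events from the start of the baseline period, may consult site staff and a sponsor systems specialist, and uses event logs and user feedback relayed by the site coordinator. The root-cause analysis looks for what, "including any aspect of the SC+ user interface, home use environment, or other factor(s), contributed to the error".

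The adjudicated result feeds a secondary safety endpoint in protocol section 6.2.2: "Number of device-related AEs and SAEs per 100 treatments in the home phase of the study, compared with those occurring in the in-clinic phase".

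**The concern.** The information the SCEC is said not to have is largely the information one of its members is told to collect. Section 14.7 gives that member no exemption from the blind, no recusal and no non-voting status.

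The blind is there to protect the attribution of events to the device. An assessor who knows that an event happened at home, with a lay user and no professional present, may judge its cause differently from the same event in clinic. If attribution shifts with phase, the device-related rates by phase are no longer a like-for-like comparison, although the protocol presents the assessment as blinded. Device-related counts are likely to be small, so a few decisions could show in the result.

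**Working it through.** The plan gives no figure on this point, so the check is mainly a comparison of texts. A short calculation then gives scale.

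**Can the blind hold for the engineer?**

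1. The blind covers the SCEC without exception, and the engineer is listed as one of its four members (section 14.7).
2. For device or user errors the engineer opens an inquiry with the clinical site (section 14.7).
3. Section 14.7 refers to the Appendix. I take the Appendix's HF specialist to be the same person. The inputs there are event logs, user feedback on what happened at the time, and possible causes that include the home setting.
4. A root cause for a use error cannot be established without knowing the user and the circumstances. The Appendix bars direct contact with participants, but the site coordinator passes on the same facts.

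Steps 1 and 2 alone conflict. Steps 3 and 4 show that the conflict cannot be avoided in practice. The answer is no.

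**Is the blind protected for the nephrologists?** Section 14.7 requires a masking review of material given to the committee. It does not say whether this covers the engineer's root-cause findings, who performs it, or whether the engineer takes part in the discussion and decision. The answer is that this is not shown either way.

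**Which events pass through this route?** Section 14.7 covers any event related to device or user error. The Appendix limits its detailed follow-up to use-related errors on critical tasks and puts non-critical errors out of scope. The two do not agree.

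**Scale.** Inputs are 33 evaluable patients and 4 home sessions per week for 8 weeks (protocol 10.2.2), and 3 clinic sessions per week for 4 to 8 weeks (protocol 6.5). Full attendance is assumed.

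- Home treatments: 33 × 4 × 8 = 1056, which matches the protocol's own total.
- Clinic treatments: 33 × 3 × 4 = 396, up to 33 × 3 × 8 = 792.
- Shift from one relabelled event = 100 / treatments in that phase.
- Home: 100/1056 = 0.09 per 100 treatments.
- Clinic: 100/396 = 0.25, or 100/792 = 0.13 per 100 treatments.

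The documents assume no device-related rate. If it were 0.5 to 2 per 100 (my assumption), 1056 home treatments would give 5.3 to 21.1 events. One relabelled home event would then change the home rate by 0.0947/0.5 = 19% down to 0.0947/2 = 5% of its value.

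**The case against.** A reader might infer that the blind fails for the whole committee and that the home-versus-clinic comparison is therefore biased. The documents do not support that, for these reasons.

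- **Masking review.** A root-cause report could well count as case material subject to the existing check, and the Appendix lets the committee set the report's format. The nephrologists may stay masked. The SCEC charter, which could hold voting rules or a firewall, is not among the documents.
- **Presenter not named.** Section 14.7 does not say that the engineer presents the event to the committee.
- **A lay user does not reveal the phase.** Patients and caregivers train in clinic and must complete three observed treatments without help (protocol 6.5), so their errors can occur in either phase. The Appendix also groups patients, caregivers and nurses under one term. Naming the user would breach the operator mask but would not by itself disclose home or clinic.
- **Direction of bias.** Protocol 9.1.2 and 9.2 tie device-relatedness to use of the device. An event put down to user error might therefore still count as device-related.
- **Stakes.** SAP 7.5 makes all secondary endpoints descriptive. The success rule (protocol 10.4, SAP 9.1) uses Kt/V and the all-AE rate, neither of which needs a device-relatedness call.

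All of this stands, and it limits the point. None of it restores the blind for the engineer, because screening documents cannot mask the person who gathered the facts. Nor does it show that the root-cause findings are screened before the nephrologists see them.

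**Conclusion.** The contradiction in section 14.7 is real. The declared blind cannot hold for one of the four SCEC members on the device- or user-error events that member investigates, and the text leaves open whether it holds for the other three.

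The consequence is confined to adjudicated device-relatedness and so to the secondary, descriptive device-related AE and SAE rates by phase. The primary safety test and the definition of trial success are untouched. Neither the size nor the direction of any bias can be determined from the documents.

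The per-event shifts calculated above rest on 33 patients, full attendance, three clinic sessions per week and no clinic period beyond 8 weeks. More patients or more treatments would make them smaller; missed sessions would make them larger. They show sensitivity and are not an estimate of bias. The point merits correction because the protocol claims a safeguard that its own procedure does not deliver, and the correction is cheap.

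**What to change.** Amend protocol section 14.7 and the SCEC charter as follows.

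1. State that the human factors engineer is an unmasked, non-voting adviser, and that the three nephrologists alone make the final device-relatedness determination.
2. State that the existing masking review covers the root-cause report. User type, setting, dates and training level are to be removed by someone other than the engineer before the nephrologists see it.
3. Reconcile section 14.7 with the Appendix on whether all device- or user-error events are investigated, or only those involving critical tasks.

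If adjudication is already complete, the study report should say that the engineer was not blinded.

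A separate determination made before the root cause is known, with rates reported both ways, is not needed. It would set aside the evidence that section 14.7 gathers for this judgment.

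The cost is protocol and charter wording, plus a small redaction step by an independent person for what should be few events.
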